4.1 Recruitment

Study information will be given to all adult patients attending weight management service at Aintree University Hospital. Eligible participants will be identified and provided with patient invitation leaflet after their clinic appointment. The researcher will verbally explain the study to the patient, confirm eligibility and hand out the patient information leaflet. Individuals who are interested in taking part will be invited back for a screening visit, in the Clinical Sciences

Centre, Aintree University Hospital. The study will be explained again at the screening visit where any questions can be answered and informed consent can be obtained. A letter will be written to the participant, their GP and their secondary care diabetes clinician at Aintree University Hospital detailing brief overview of the trial.

4.2 Inclusion criteria

- Man or woman, 18 to 70 years of age, inclusive
- BMI ≥ 30 kg/ m² to ≤ 60 kg/m² at screening visit
- Stable weight (ie, change of < 5% within 12 weeks before screening based on medical history)
- Subjects are in the investigators opinion, well-motivated, capable, and willing to learn how to undergo indirect calorimetry testing, as required for study
- Willing and able to adhere to the prohibitions and restrictions specified within this protocol

4.3 Exclusion criteria

- Taking weight loss medication within 12 weeks prior to randomisation
- Previous or planned bariatric surgery
- History of Type 1, Type 2 diabetes mellitus, DKA or diabetes secondary to pancreatitis
- Has a HbA1c of $\geq 6.5\%$ (or ≥ 48 mmol/mol)
- History of obesity with a known secondary cause (e.g. Cushing's disease / syndrome)
- Oral corticosteroid use (except in the short term use of a 7-10 day course)
- Ongoing, inadequately controlled thyroid disorder defined as thyroid-stimulating hormone >6 mIU/litre or <0.4 mIU/litre
- History of malignancy within 3 years before screening (or diagnosis of malignancy within this period)
- eGFR ≤ 30 ml/min/1.73m² on serum testing
- Alanine aminotransferase level is >2.0 times the upper limit of normal or total bilirubin is >1.5 times the upper limit of normal at screening
- Other major illness likely to preclude participation in the trial
- History of glucagonoma

- An MI, unstable angina, revascularization procedure (stent or bypass graft surgery) or cerebrovascular accident within 12 weeks before screening
- Heart Failure NYHA Class III-IV
- End-stage Chronic Obstructive Pulmonary Disease (COPD)

4.4 Sample size

Previous studies in this population from Aintree LOSS(33) community-based, multidisciplinary weight management programme for patients with severe and complex obesity, demographic data of patients who attended had an average weight loss of 1.29 kg (+/- SD 4.88) and mean BMI of 45.6 (+/- SD 6.8) kg/m². The study will have 80% power to detect additional weight loss of 3 kg between the SC and ECAL group. This difference is taken from cornerstone studies like the Diabetes Prevention Programme, which suggests a weight loss of 3-5% of initial body weight would lead to risk reduction in progression of diabetes. Using a power calculator with SD above, the sample size is 42 patients per group; hence n = 84 patients (primary outcome). Allowing for attrition rate of 20%, the sample size required would be $84 / 0.80 = 105$ patients.

4.5 Withdrawal criteria

Participants may withdraw consent from the study before study completion if they decide to do so, at any time and for any reason. If a participant decides to withdraw from the study, this will be recorded in the study records. They will be sent a letter thanking them for their participation, and informing them that the data collected up to the time point they withdrew will be included in the study analysis and that they will not be contacted again with regards to this study. They will not be asked to attend further visits. Furthermore, we will emphasise that their standard care will not be affected by their withdrawal from this study and that they will return to standard care.

Participants will be withdrawn from this study by the research team as agreed by the PI if:

- They are diagnosed with a terminal illness
- The PI, sponsor or study clinician deem it unsafe for continuation in the study for medical, safety, regulatory or other reasons consistent with applicable laws, regulations, or Good Clinical Practice (GCP)
- They are considered to be lost to follow-up as deemed by the clinician.
- Loss of capacity during participation in research
- Treatment with medications which the PI determines to require permanent withdrawal from the study (e.g. systemic corticosteroids)

[figure not shown]
- Female participants with a positive pregnancy test

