2.2 Secondary Objectives

1. To establish the acceptability and reproducibility of using indirect calorimetry to measure energy expenditure as compared to use of standard predictive energy equations.
2. To determine whether metabolic parameters of REE or RQ are potential surrogate biomarkers to predict weight loss.

3 Study design

Type of study: Randomized-controlled trial

Primary endpoint

Reduction in body weight from baseline to end-of treatment (24 weeks)

4. Study population

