5.2 Baseline visit & Randomisation

Eligible participants will be able to proceed to the Baseline Visit (Week 0). Weight, blood pressure and pulse rate will be recorded for all patients in line with study SOPs. The patient will also complete questionnaires to provide demographic and medical history details and additional data will be collected. Participants will be counselled about the study visits and provided with a food diary to record their food intake during the week. Participants will each receive support from the dieticians and weight management practitioners and/or clinicians with regards to maintaining reduced calorie intake according to their respective groups. Participants may contact their study team or GP at any time.

Eligible participants will then be randomly assigned to one of two groups in a 1:1 ratio:

- 1) The *control group* (SC) – standard care including diet, exercise and behaviour modification therapy. Energy expenditure information (RMR, RQ) measured from IC will be **withheld** from participants until the final visit. Participants will receive a standard nutritional energy goal based on the Harris-Benedict equation, the standard predictive equation used at Tier 3 weight management service at Aintree University

Hospital. Both participants and the study clinician providing advice and care will be “blinded” to the client and practitioner report until the completion of the final visit (week 24). To maintain the “blinding” of both participant and clinician in the SC group, the IC measurement is performed and an electronic copy of this is stored in the database, without showing the report to the participant or clinician. Upon completion of the final visit, SC group participants will be able to request a copy of the relevant client reports, should they wish to do so.

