6.2 Statistical Analysis

Patient characteristics and clinical data will be analysed using SPSS software and STATS Direct. Normally distributed data will be expressed as mean +/- standard deviation (SD). Categorical variables will be analysed by using Chi-squared testing. Continuous variables between groups will be evaluated with unpaired student's t-test (if normal distribution) or Mann-Whitney U test (if not normally distributed). P values < 0.05 will be considered significant.

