7.2.2 Serious AEs

An SAE form should be completed and faxed to the Chief Investigator within 24 hours. However, relapse and death due to <condition>, and hospitalisations for elective treatment of a pre-existing condition do not need reporting as SAEs.

All SAEs should be reported to the <name of REC> where in the opinion of the Chief Investigator, the event was:

- 'related', i.e. resulted from the administration of any of the research procedures; and
- 'unexpected', i.e. an event that is not listed in the protocol as an expected occurrence

Reports of related and unexpected SAEs should be submitted within 15 days of the Chief Investigator becoming aware of the event, using the NRES SAE form for non-IMP studies. The Chief Investigator must also notify the Sponsor of all SAEs.

Local investigators should report any SAEs as required by their Local Research Ethics Committee, Sponsor and/or Research & Development Office.

Contact details for reporting AEs

Please send SAE forms to:
Research and Development,
Third Floor Clinical Sciences Building,
University Hospital Aintree,
[name],
Liverpool
[name]
[contact]
[contact]

8 Assessment and Follow-up

All participants should currently be registered with a weight management service. Should they require follow up after the study, they will return to their registered weight management service provider for any follow-ups.

9 Regulatory issues

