9.2 Consent

Consent to enter the study must be sought from each participant only after a full explanation has been given, an information leaflet offered, and time allowed for consideration. Signed participant consent should be obtained. The right of the participant to refuse to participate without giving reasons must be respected. After the participant has entered the study the clinician remains free to give alternative treatment to that specified in the protocol at any stage if he/she feels it is in the participant's best interest, but the reasons for doing so should be recorded. In these cases, the participants remain within the study for the purposes of follow-up and data analysis. All participants are free to withdraw at any time from the protocol treatment without giving reasons and without prejudicing further treatment.

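### Section 4.5 gives a participant who decides to withdraw only a full exit, so someone who would still accept a final weighing has no route to provide the week-24 primary outcome

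*Protocol*

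**What the plan says.** **Protocol 4.5 (Withdrawal criteria).** The rule opens with participants withdrawing consent from the study, at any time and for any reason. Such a participant is sent a letter, data up to the withdrawal date stay in the analysis, and there is no further contact about the study. "They will not be asked to attend further visits". They return to standard care. No lesser option is described.

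**Protocol 9.2 (Consent).** If the clinician departs from the protocol treatment in the participant's interest, the participant stays in for follow-up and analysis. The section then adds: "All participants are free to withdraw at any time from the protocol treatment without giving reasons and without prejudicing further treatment". It does not say whether people who use that right are still followed up.

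**Protocol 3 (Primary endpoint).** The wording is "Reduction in body weight from baseline to end-of treatment (24 weeks", with the bracket closing after the number of weeks. Anyone leaving earlier under 4.5 has no week-24 value.

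**Protocol 8 (Assessment and Follow-up).** Participants should be registered with a weight management service, and if they need follow-up after the study, "they will return to their registered weight management service provider for any follow-ups".

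**Protocol 4.4 (Sample size).** "The study will have 80% power to detect additional weight loss of 3 kg between the SC and ECAL group". The figures are SD 4.88 kg, 42 per group, 84 in total, and 105 after allowing for 20% attrition.

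**The concern.** Stopping a demanding study procedure and withdrawing consent to any further data are different decisions. Section 9.2 names the first and section 4.5 handles only the second. Both arms are scheduled for nine fasted calorimetry sessions (weeks 0, 1, 2, 4, 8, 12, 16, 20 and 24). It is easy to picture a participant who has had enough of these but would be willing to stand on a scale at week 24. When that person says they want to stop, the only procedure the protocol describes is full exit.

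Two things are at stake. The first is a primary outcome value that could have been collected. The second is bias. How well a weight programme is going may well influence whether a person stays in it. Reasons for stopping could also differ by arm, because ECAL participants receive their readings at each visit while SC participants take the same tests with results withheld until the final visit. Whoever is or is not weighed at week 24 is settled by trial conduct. An analysis plan can model a missing weight, but it cannot recover one that was never taken.

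**Working it through.** **1. The plan's own figure.** Inputs from 4.4 and 6.2: difference 3 kg, SD 4.88 kg, power 80%, "P values < 0.05 will be considered significant" (taken as two-sided 0.05; a one-sided test would give 33 per group and does not match), allocation 1:1.

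n per group = 2 × (1.960 + 0.842)² × 4.88² / 3² = 41.5, rounded up to 42. Total 84, and 84 / 0.80 = 105. The stated figures reproduce. Power at 42 per group is 80.4% by the normal approximation (79.5% by the noncentral t). The allowance corresponds to 105 − 84 = 21 missing weights.

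**2. Precision.** SE of the difference = 4.88 × √(2/n). The SE rows use n = 42, 47 and 52.5; power is for 105 randomised (normal approximation).

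| Week-24 weights missing | n per arm | SE (kg) | Power for 3 kg |
|---|---|---|---|
| 20% | 42 | 1.065 | 80.4% |
| 10% | about 47 | 1.007 | 84.8% |
| 0% | 52.5 | 0.952 | 88.3% |

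The first row is the plan. Recovered weights add precision above it, so precision shows no shortfall.

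**3. Bias.** Let d be the share of an arm without a week-24 weight, and g the amount by which those people lost less weight than the rest of their arm. The mean loss in the whole arm equals the mean in those observed minus d × g. If only observed week-24 weights are compared, then

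error in the ECAL minus SC difference = d(ECAL) × g(ECAL) − d(SC) × g(SC).

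All values of g, and every unequal dropout split, are assumptions; the protocol gives none.

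| Dropout, ECAL / SC | Gap g, ECAL / SC (kg) | Error (kg) |
|---|---|---|
| 20% / 20% | equal gaps | 0 |
| 20% / 20% | 4 / 1 | 0.20 × (4 − 1) = 0.6 |
| 25% / 15% | 1 to 4, same in both | 0.10 × g = 0.1 to 0.4 |
| 30% / 10% | 1 to 4, same in both | 0.20 × g = 0.2 to 0.8 |
| 15% / 25% | 1 to 4, same in both | −0.1 to −0.4 |
| 10% / 30% | 1 to 4, same in both | −0.2 to −0.8 |

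The 0.6 kg case is 0.6 / 3 = 20% of the target difference. A positive sign overstates the benefit of ECAL and a negative sign understates it.

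**4. Partial recovery.** Take the 0.6 kg case and suppose half of the missing weights in each arm are obtained, from people typical of all those who left. The arm then has 80% who stayed and 10% recovered. The observed mean falls by (0.10 / 0.90) × g instead of the full 0.20 × g. The remaining error is (0.20 − 0.111) × (4 − 1) = 0.27 kg. Recovering half therefore removes a little more than half of the error under these assumptions.

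**The case against.** The strongest reply is that 4.5 is written for withdrawal of consent from the study, and ending contact is right for that group. Nothing in 4.5 says that a person who misses or tires of calorimetry must be withdrawn, and non-adherence is not among the reasons for withdrawal by the research team. Section 9.2 also already keeps people in follow-up when the clinician changes treatment. All of this stands. It narrows the point to the participant who chooses to stop, for whom neither section offers anything between full participation and full exit.

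A reader might infer several stronger things that the protocol does not support:

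- **That the primary comparison is restricted to those who stayed.** This is not stated. Data up to withdrawal are to be included, weight is measured before each calorimetry session, so most leavers should have serial weights, and their handling may be set out in an analysis plan that is not shown.
- **That the endpoint date is ambiguous for someone who stops early.** The bracketed 24 weeks fixes the time point, and the synopsis describes a 24-week trial.
- **That the missing weights can be had from the clinic at almost no cost.** No section says that a routine weight is taken near week 24 or that leavers keep attending, and section 8 speaks of follow-up only if required. The consent form is not available to check whether it covers routine records.
- **That the sample size is too small.** It is not; the 20% loss is budgeted.

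Finally, the 20% is not broken down. It may include loss to follow-up, terminal illness, pregnancy, loss of capacity and full withdrawal of consent, most of which the change would not recover.

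**Conclusion.** The point holds as an inexpensive improvement in trial conduct, together with a need to reconcile 4.5 with 9.2. It is not an error in any stated figure and not a demonstrated bias. Followed as written, the protocol can lose week-24 weights that some participants would have been willing to give.

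The size is unknown. It is zero if dropout and gaps are the same in both arms, 0.6 kg with 20% stopping in each arm and assumed gaps of 4 kg and 1 kg, and between 0.1 and 0.8 kg in either direction under the other assumed splits. These figures describe a comparison of observed week-24 weights only, which the protocol does not prescribe. They count all attrition, so they are an upper limit on what the change could correct under the same assumptions. The attrition allowance protects power up to 20% loss but does nothing about bias.

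**What to change.** In 4.5, separate two decisions:

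- **(a)** The participant stops the allocated advice, the calorimetry, or both, but agrees to one week-24 weight, or to use of a routine clinic weight near week 24 if one exists and consent covers it.
- **(b)** The participant withdraws consent to all further data. The present no-contact rule stays as it is.

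Offer (a) first, with (b) always open. Align 9.2 so that participant-initiated withdrawal from treatment keeps follow-up in the same way as a change made by the clinician. State beside the primary endpoint that the week-24 weight is collected whether or not the programme was stopped. Record which level each participant chose, and the source and date of any weight not taken at the study visit. None of this alters when or why a participant may stop.

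The cost is a protocol amendment and, if consent does not already cover it, a line in the information sheet and consent form. No new procedure is needed. The small downside is that some recovered weights may come from other scales, or from dates near rather than at week 24.

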5.9 Indirect Calorimetry

(Week 0, 1, 2, 4, 8, 12, 16, 20 and 24 weeks)

Preparing for the Test

Participants will be advised to abstain from food and alcohol for 7 hours or greater before the IC measurement. Participants will be advised to avoid stimulants and stressors such as caffeine, nicotine, and tobacco for at least 4 hours prior to the test. Beverages allowed include water, caffeine-free and calorie-free drinks. A standard operating procedure for ECAL indirect calorimetry will be adhered to as attached in Appendix.

Steady State Testing

After measuring their height, weight, and other anthropometric data, the participant will lie supine with head elevated 30 degrees, extended limbs in a silent room. In line with safety measures for current COVID19 pandemic, patients will be asked to sit behind a transportable Perspex screen. Using the screen will prevent large droplet dispersal and protect the staff member and surrounding area. Whilst lying in a physically comfortable position, the participant will be asked to maintain a regular inspiratory pattern, avoid moving and speaking during the test. Participant will be advised to remain rested for at least 10 minutes. The mouthpiece will be held with either hand, and participant will be required to breathe through the mouthpiece, with a single-use nose clip applied over the nostrils. The mouthpiece has a two-way filter and will be single-use only. Upon completion it will be disposed of in the clinical waste bin.

REE will be measured using the ECal Indirect calorimetry (Metabolic Health Solutions, Australia) at participant’s bedside. Gas and volume calibration of the device will be performed before each measurement. A mouthpiece will be used to measure inspired oxygen and expired carbon dioxide for up to 6-10 minutes, with the first 2 minutes of data discarded. REE (kcal/day) is calculated by the ECal device. Patients were considered to have reached a steady-state REE if a minimum of 5 consecutive minutes with less than 10% coefficient of variation in VO₂ and VCO₂ was achieved; otherwise repeat testing was indicated.

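### The two-group tests fixed in Section 6.2 use neither baseline weight as a covariate nor the interim weights, and Sections 4.5 and 9.2 give opposite instructions for some participants on non-protocol treatment

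*Protocol*

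**What the plan says.** **Endpoint and test.** Section 3 defines the primary endpoint as "Reduction in body weight from baseline to end-of treatment (24 weeks"). Section 6.2 states: "Continuous variables between groups will be evaluated with unpaired student's t-test" when the data are normally distributed, and Mann-Whitney U otherwise. It names no covariate and no repeated-measures model.

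**Weights available.** Section 5.9 has weight taken before each calorimetry test: "After measuring their height, weight, and other anthropometric data, the participant will lie supine". Sections 5.4 and 5.5 schedule calorimetry in both arms at weeks 0, 1, 2, 4, 8, 12, 16, 20 and 24.

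**Leaving the study.** Section 4.5 lists grounds on which the research team withdraws a participant, among them "Treatment with medications which the PI determines to require permanent withdrawal from the study (e.g. systemic corticosteroids"). Of participants who decide to withdraw, the same section says that their data up to that point will enter the analysis and that no further visits are requested. It says neither of participants removed by the team.

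**Staying in the study.** Section 9.2 says "the clinician remains free to give alternative treatment to that specified in the protocol at any stage" if that is in the participant's interest, and then: "In these cases, the participants remain within the study for the purposes of follow-up and data analysis". It also separates stopping treatment from leaving the study: "All participants are free to withdraw at any time from the protocol treatment".

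**Related entry rule.** Section 4.3 excludes people for "Taking weight loss medication within 12 weeks prior to randomisation". Section 4.5 does not say what follows if such a medicine is started after randomisation.

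**The concern.** There are two linked weaknesses, both bearing on the primary endpoint.

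First, a two-group test on 24-week change needs a week-24 weight. A participant who leaves at week 16 has six interim weights on file (weeks 1, 2, 4, 8, 12 and 16), yet contributes nothing to the test unless the week-24 value is imputed. That sits badly with the statement in Section 4.5 that data collected before a participant withdraws will be included. With 20% attrition planned, the unused information is not trivial.

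Second, Sections 4.5 and 9.2 disagree on whether some participants are followed at all. Participants know their allocation (Section 5.3) and some grounds for removal are discretionary, so removals could differ between arms. Starting another weight treatment is likely to be related to the outcome. If the week-24 weight is not sought, an analysis plan written later may have nothing to work with.

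**Working it through.** **1. The plan's own figure.** Section 4.4 gives a 3 kg difference, SD 4.88 kg and 80% power. Section 6.2 gives 5% significance, taken here as two-sided.

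n per group = 2 × (1.960 + 0.842)² × 4.88² / 3² = 41.5, so 42. The total is 84, and 84 / 0.80 = 105. The stated figures reproduce.

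**2. The stated test at the planned attrition.** 105 / 2 = 52.5 per arm randomised, and 0.80 × 52.5 = 42 with a week-24 weight.

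SE = 4.88 × √(2/42) = 1.06 kg. Power for 3 kg = Φ(3/1.065 − 1.96) = 0.80.

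**3. Baseline weight as a covariate.** Baseline is already in the change score by subtraction. Adjustment multiplies the residual variance by 1 − r², where r is the correlation of baseline weight with change. The documents do not give r. For an assumed r of 0.1 to 0.3, variance falls by 1% to 9%, and power at 42 per group becomes 0.808 to 0.840.

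**4. Using the interim weights.** Assumptions: 52.5 per arm; SD of change 4.88 kg at week 24; 20% leavers spread evenly over the eight intervals between visits, so 2.5% in each; leaving unrelated to the observed weights. With V the covariance of the eight post-baseline changes and V_k its block for those seen at the first k visits:

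- information per arm: I = Σ 52.5 × p_k × V_k⁻¹, with p_k = 0.025 for k below 8 and 0.80 for k = 8
- SE of the week-24 contrast = √(2 × [I⁻¹] at week 24)
- effective patients per arm = 2 × 4.88² / SE²
- power = Φ(3/SE − 1.96)

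The last column assumes that leavers drift from stayers steadily from week 0. It gives the share of the completers' bias that the model leaves in place.

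| Assumed pattern of V | SE (kg) | Effective n per arm | Power | Bias left |
|---|---|---|---|---|
| Random slope, 1 kg noise | 1.00 | 47 | 0.85 | 42% |
| Random slope, 2 kg noise | 1.03 | 45 | 0.83 | 58% |
| Random slope, 3 kg noise | 1.05 | 43 | 0.82 | 72% |
| Random walk | 1.03 | 45 | 0.83 | 64% |
| 4-week autocorrelation 0.9 | 1.02 | 46 | 0.84 | 71% |
| 4-week autocorrelation 0.7 | 1.05 | 43 | 0.81 | 83% |
| Equal correlation 0.5 | 1.03 | 45 | 0.83 | 86% |
| Equal correlation 0.7 | 1.00 | 47 | 0.85 | 84% |

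If the gap opens only after leaving, 100% of the bias is left in every row. The gain in step 3 is not included in this table.

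**5. The two sections side by side.**

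| Situation | Section 4.5 | Section 9.2 |
|---|---|---|
| Non-protocol treatment that the PI does not judge to require withdrawal | does not apply | kept in follow-up and analysis |
| Medication that requires withdrawal but is not alternative treatment | removed | does not apply |
| Both at once | removed | kept in follow-up and analysis |

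Only the last row is a contradiction, and neither section refers to or excepts the other. A corticosteroid course for an unrelated illness may belong in the second row. A weight-loss medicine started during the trial could fall in the third if the PI judged it to require withdrawal.

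**6. Scale of the overlap.** The documents give no count of such removals. As scale only: if m more participants are removed in one arm than in the other, and they differ from stayers by d kg, a completers' comparison shifts by (m/52.5) × d. With m = 1 and d = 1.29 kg this is 0.02 kg. With m = 5 and d = 4.88 kg it is 0.46 kg. The sign may go either way, and the shift is zero if numbers and gaps match between arms. Here m and d are assumed; 1.29 and 4.88 are the mean loss and SD in Section 4.4, borrowed as units.

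**The case against.** **The stated test is legitimate.** An unadjusted comparison of change is valid under randomisation with complete data, and it matches the sample size, which uses the SD of change. This stands. A reader might infer that the tests ignore baseline weight; they do not, because the endpoint subtracts it. Only covariate adjustment is absent.

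**The analysis plan may settle this.** Analysis sets and missing-data rules are commonly left to a statistical analysis plan, which is not at hand. Their absence is not held against the protocol. The protocol does, however, name the test, and a named method can be improved. Who is followed up is a matter of trial conduct and belongs in the protocol.

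**The overlap is narrow.** It needs a treatment that is both alternative to the protocol and judged by the PI to require withdrawal. Section 4.5 could be read as a specific exception to the general clause in Section 9.2. The narrowness stands, but the text does not state that exception. For the other team removals the protocol is silent rather than contradictory, and for several of those grounds a week-24 weight would often be unobtainable or hard to interpret.

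**The weight may exist anyway.** Participants return to their registered weight management service (Section 8), so a routine weight near week 24 may be on record. That is fair, but it would be an unplanned measurement.

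**Conclusion.** The point holds in two limited parts.

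The method in Section 6.2 is valid but wasteful. Under the assumed correlations and 20% dropout, a baseline-adjusted repeated-measures model lowers the standard error from 1.06 kg to about 1.00 to 1.05 kg and raises power for 3 kg from about 80% to 81-85%. The gain is modest. Protection against informative dropout is partial: 42% to 86% of the bias remains if the gap opens steadily, and all of it if the gap opens only after leaving.

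Sections 4.5 and 9.2 contradict each other for participants who meet both rules. The size and direction of any resulting bias cannot be set from the documents. The 0.02 to 0.46 kg in the working is scale under assumed inputs, not an estimate.

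Two stronger readings are not supported. One is that the planned 20% attrition measures the damage from this conflict; that figure covers all dropout, whatever its cause. The other is that obtaining a week-24 weight removes the bias fully. It does so only if weight regardless of other treatment is the quantity wanted, and the protocol does not say that it is. No figure in Section 4.4 is wrong on this point.

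**What to change.** 1. **Section 6.2.** Make the primary analysis a repeated-measures mixed model by randomised group on the scheduled weights, with baseline weight as covariate and the week-24 contrast as primary. Add a sensitivity analysis for the missing-at-random assumption, for example shifting leavers' week-24 weight by 0 to 4.88 kg separately in each arm, in both directions.
2. **Sections 4.5 and 9.2.** Reconcile them, with a cross-reference. State that removal by the research team does not by itself end outcome collection, and that the week-24 weight is sought where consent stands, capacity is retained and the participant can be reached. State also how weights taken after such removals enter the analysis. Which medications or events lead to removal stays with the investigators. Ending contact after a participant withdraws consent is not in question.

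**Cost.** Wording in three sections, slightly more analysis work, and a missing-at-random assumption that the sensitivity analysis must test. No extra patients are needed. A few removed participants would need a week-24 weight they might otherwise not have given.
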